8.1.1.2 Local Site Reactions

Investigator or designee will assess treatment area and rate on a scale of 0 = absent, 1 = mild (slight, barely perceptible), 2 = moderate (distinct presence), and 3 = severe (marked, intense) the following at Visits 2 and 3:

- Erythema
- Petechiae
- Erosion/ulceration
- Edema

The subject will be queried by the Investigator or designee for presence of the following and, if present, the subject will be asked to rate as described above:

- Burning/stinging
- Pain
- Pruritus (itching)

Local site reactions will be collected independently of AEs and will include any reaction that occurs within the treatment area. Local site reactions that require medical intervention (e.g., prescription medication) or extend beyond the treatment area should be documented as an AE.

8.1.1.3 Serious Adverse Events (SAEs)

An AE is considered "serious" if, in the view of either the investigator or sponsor, it meets the criteria for any of the following outcomes:

1. Death.
2. Life-threatening. This term refers to an event in which the participant was at risk of death at the time of the event; it does not refer to an event that hypothetically might have caused death if it were more severe.
3. Requires inpatient hospitalization or prolongation of existing hospitalization. In general, hospitalization signifies that the participant has been admitted (usually involving at least an overnight stay) at the hospital or emergency ward for observation and/or treatment that would not have been appropriate in the physician's office or outpatient setting.

Complications that occur during hospitalization are AEs or SAEs as defined above. If a complication prolongs hospitalization or fulfills any other serious criteria, the event is serious. When in doubt as to whether “hospitalization” occurred or was necessary, the AE should be considered serious. Hospitalization for elective treatment or procedures of a pre-existing condition that did not worsen from baseline is not considered an AE.

4. Results in persistent or significant disability/incapacity. The term disability means a substantial disruption of a person’s ability to conduct normal life functions. This definition is not intended to include experiences of relatively minor medical significance such as uncomplicated headache, nausea, vomiting, diarrhea, influenza, and accidental trauma (e.g., sprained ankle) which may interfere or prevent everyday life functions but do not constitute a substantial disruption.
5. Is a congenital anomaly/birth defect.

Medical or scientific judgment should be exercised in deciding whether (expedited) reporting is appropriate in other situations, such as important medical events that may not be immediately life-threatening or result in death or hospitalization but may jeopardize the participant or may require medical or surgical intervention to prevent one of the other outcomes listed in the above definition. These medically important events should also be considered SAEs. Examples of medically important events are intensive treatment in an emergency room or at home for allergic bronchospasm; blood dyscrasias or convulsions that result in hospitalizations; or development of drug dependency or drug abuse.

In addition, cancer and drug overdose are included in [REDACTED] classification of an SAE.

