3.5.3.2 Warnings

3.5.3.2.1 Convulsive Seizures and Peripheral Neuropathy

Convulsive seizures and peripheral neuropathy, the latter characterized mainly by numbness or paresthesia of an extremity, have been reported in patients treated with oral or intravenous metronidazole. The appearance of abnormal neurologic signs demands the prompt discontinuation of metronidazole vaginal gel therapy. Metronidazole vaginal gel should be administered with caution to patients with CNS diseases.

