8.1.3.2 Recording of Adverse Events

AEs will be reported in the EDC system using a recognized medical term or diagnosis that accurately reflects the event. Information recorded in the EDC system must be substantiated in the source documents. All AEs must be recorded in the participant's source documents and must include the following information (when applicable):

- Specific condition or event.
- Possible etiologies and whether the event meets criteria as an SAE and therefore requires immediate notification to the sponsor. (See [Section 8.1.1.3](#) for the definition of SAEs.)
- Indication of whether the condition was preexisting prior to study entry or not and if yes, whether it has worsened in severity or frequency, in which case it is reported as an AE. Conditions present prior to study entry that do not worsen in severity are not considered AEs.
- Date of occurrence.
- Date of resolution. If the event has not resolved at the end of the study-reporting period, it will be reported as still present in the EDC system.
- AEs that change in intensity are recorded at the most severe intensity level that is reported by the participant.
- Relationship to study product as evaluated by the investigator (causality assessment).
- Action taken with the study product per the investigator medical judgment (study product interrupted, discontinued or none) and outcome.
- Seriousness: An SAE, in accordance with 21 CFR 312.32 (a), means “any adverse event occurring at any dose that results in any of the following outcomes: death, a life threatening adverse drug experience, inpatient hospitalization or prolongation of existing hospitalization, a persistent or significant disability/incapacity or a congenital anomaly/birth defect. Important medical events that may not result in death, be life-threatening or require hospitalization may be considered a serious adverse drug experience when, based upon appropriate medical judgment, they may jeopardize the patient or subject and may require medical or surgical intervention to prevent one of the outcomes listed in this definition. Examples of such medical events include allergic bronchospasm requiring intensive treatment in an emergency room or at home, blood dyscrasias or convulsions that do not result in inpatient hospitalization or development of drug dependency or drug abuse.” In addition, cancer and drug overdose are included in [REDACTED] classification of an SAE.

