8.1.3.3 Notification to Sponsor of Serious Adverse Events

All SAEs will be reported promptly in accordance with the FDA regulations and recorded on the appropriate forms.

**WHEN ANY SAE, REGARDLESS OF RELATIONSHIP TO THE STUDY PRODUCT, IS
ENCOUNTERED DURING THIS CLINICAL TRIAL AT AN INVESTIGATOR'S SITE,
THE INVESTIGATOR, IN ACCORDANCE WITH 21 CFR 312.64(b), MUST NOTIFY
[REDACTED] WITHIN 24 HOURS OF IDENTIFICATION/AWARENESS OF
THE SAE BY REPORTING THE EVENT VIA THE EDC SYSTEM AND VIA THE SAE
REPORTING FORM FOR THIS STUDY. SAE SUBMISSION SHOULD BE
COMPLETED FOR ANY SAE THAT IS EXPERIENCED AFTER THE SUBJECT HAS
SIGNED THE ICF, EVEN IF INVESTIGATIONAL PRODUCT HAS NOT YET BE
ADMINISTERED.**

The investigator should complete the AE eCRF within the EDC system and mark the AE as serious which will send the appropriate notifications to the Medical Monitor as well as the appropriate [REDACTED] staff. The clinical investigator is to also send an SAE Report Form by email to [REDACTED]

All SAEs whether or not thought related to the study drug, must be reported by the Study Investigator (by telephone, fax or email) to [REDACTED] within 24 hours of the investigator becoming aware of the event.

SAE reports should be sent to:

The investigator or responsible site staff will enter all AEs into the eCRF as delineated above. AEs that are assessed as serious also require the completion of a separate SAE report. Following receipt of the SAE report, the SAE reporting contact will review.

Additional supporting documentation for SAEs (i.e. hospital discharge summary, lab report, etc.) which should be provided whenever possible (with participant name redacted) to verify the medical diagnosis includes hospital discharge summaries and death certificates/autopsy reports (where applicable), surgical procedure summaries, histology reports, and imaging reports should be uploaded to the study document repository or [REDACTED] EDC page as outlined in the Study Procedures Manual within three days of receipt at the site. [REDACTED] will ensure appropriate copies of supporting document are provided to the Medical Monitor.

NOTE: Investigators should not wait to collect the additional information needed to fully document the event before submission of an SAE.

The SAE report will be sent immediately to the Sponsor for assessment and report to health authorities where appropriate. Treatment or laboratory tests will be conducted at the discretion of the Investigator.

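### The example of a medically important event in Protocol 8.1.1.3 contradicts 8.1.3.2 and its own lead sentence, and may steer sites to grade a non-hospitalised convulsion as non-serious

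*Protocol*

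**What the plan says.** Protocol 8.1.1.3 lists five outcomes that make an adverse event serious. The third is hospitalisation: "Requires inpatient hospitalization or prolongation of existing hospitalization". After the list, a general clause extends the definition by medical judgment to other situations, "such as important medical events that may not be immediately life-threatening or result in death or hospitalization but may jeopardize the participant", and states that "These medically important events should also be considered SAEs". Examples follow, among them "blood dyscrasias or convulsions that result in hospitalizations; or development of drug dependency or drug abuse".

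Protocol 8.1.3.2 tells sites what to record for each adverse event and refers them back to 8.1.1.3 "for the definition of SAEs". Under its item on seriousness it also sets out a full definition attributed to 21 CFR 312.32(a). The matching example there reads "blood dyscrasias or convulsions that do not result in inpatient hospitalization or development of drug dependency or drug abuse".

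Protocol 8.1.4 also cites 8.1.1.3 when it says which laboratory results must be reported as SAEs. Protocol 8.1.3.3 requires every SAE to be reported "within 24 hours of the investigator becoming aware of the event". SAP 3.8.2 lists medically important events as one kind of SAE but gives no examples, so it does not settle the difference.

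**The concern.** The two protocol sections use the same example with opposite conditions. A reader who takes the 8.1.1.3 example at face value would conclude that a convulsion belongs in the medically important category when it leads to admission. By implication, one managed without admission would not belong there.

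The grading has consequences. SAE status starts the 24-hour notice (8.1.3.3), brings notification of the institutional review board (8.1.3.4), places the event in the SAE listing (Protocol 9.7.4, SAP 3.8.2) and requires a narrative (Protocol 9.7.1). Safety and tolerability form the secondary objective. The example also concerns a labelled warning for this drug, since Protocol 3.5.3.2.1 reports that "Convulsive seizures and peripheral neuropathy, the latter characterized mainly by numbness or paresthesia of an extremity, have been reported in patients treated with" the oral or intravenous forms. With about 40 sites making the first call on seriousness, a single consistent definition is what keeps that call uniform.

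**Working it through.** The point is textual. The protocol states no figure to reproduce, and no formula applies. The documents give no rate of convulsion or blood dyscrasia for the gel, so no expected count is calculated.

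**1. The two examples side by side.**

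| Section | Condition attached to the convulsion example |
|---|---|
| Protocol 8.1.1.3 | leads to hospitalisation |
| Protocol 8.1.3.2 | does not lead to inpatient hospitalisation |

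The most natural reading attaches the condition to blood dyscrasias as well. Even on the narrower reading, where it qualifies convulsions alone, the contradiction remains.

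**2. The 8.1.1.3 example against its own lead sentence.** The clause being illustrated concerns events that may be important without hospitalisation. An example that requires hospitalisation does not illustrate it. The neighbouring example, bronchospasm treated in an emergency room or at home, does fit.

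**3. What each example adds to criterion 3.**
- A hospitalised convulsion is already serious under criterion 3, so the 8.1.1.3 example adds no event.
- A non-hospitalised convulsion is not covered by criterion 3. The 8.1.3.2 example adds such events where medical judgment finds that they may jeopardise the subject and may need intervention to prevent a listed outcome.

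The wording of 8.1.1.3 is therefore redundant where it applies and silent on the case the category exists for. A dropped *not* is the likeliest explanation, though that is inference.

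**4. Which text a site would use.** Sections 8.1.3.2 and 8.1.4 both send the reader to 8.1.1.3. No passage says which wording prevails where the two differ.

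**5. What happens if such an event is graded non-serious.**
- It is still recorded, because 8.1.1.4 requires all adverse events to be reported.
- It does not start the 24-hour clock and does not enter the SAE listing.
- It gets no SAE narrative. Protocol 9.7.3 would still require one if the event led to discontinuation.
- The reconciliation in 8.1.3.5 matches SAE forms to the database, and source review looks for unreported events. Neither step is described as checking the seriousness grade of an event already recorded.
- The Medical Monitor's periodic blinded review of adverse events (SAP 3.1.1) could find it, but nothing ties that review to 24 hours.

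**The case against.** The strongest reply is that the operative rule is intact and only one illustration is faulty. The general clause in 8.1.1.3 covers events without hospitalisation and says they should be treated as SAEs. An example list excludes nothing, and 8.1.3.2 names the non-hospitalised convulsion directly. This stands, and it limits the point to a risk of misgrading.

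Other text narrows the gap further.
- Criterion 3 generally counts admission to an emergency ward, and treats an event as serious when it is doubtful whether hospitalisation occurred or was necessary.
- Seriousness may be decided in the view of either the investigator or the sponsor, so the sponsor can upgrade an event.
- Section 13 requires prompt reporting of all adverse events, and 8.1.3.5 has safety data reviewed throughout the study.

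These are real safeguards against an event going unseen. They do not guarantee that it is reported as an SAE within 24 hours.

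The drug-specific weight is also modest. The seizure warning comes from oral or intravenous use. The appended label puts the gel's mean peak serum level at about 2% of that after a 500 mg oral dose. Treatment lasts 5 days, and a history of CNS-related disorders is an exclusion. Convulsions do not appear among the gel-trial reactions reproduced in 3.5.3.4.1. The schedule of assessments includes no haematology, so a blood dyscrasia would come to light only incidentally. All of this bears on how often the error could matter, not on whether it is there.

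Two stronger readings are tempting, and the documents support neither. A reader might infer that 8.1.1.3 removes non-hospitalised convulsions from SAE reporting; its general clause says otherwise. A reader might also infer that 8.1.3.2 makes every such convulsion or dyscrasia an SAE; it says only that they may be considered serious on appropriate medical judgment.

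**Conclusion.** Wrong as written (minor). The contradiction between 8.1.1.3 and 8.1.3.2 is exact, and it sits in the section the protocol cites for its SAE definition. The faulty example also conflicts with its own lead sentence and duplicates criterion 3.

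The effect is confined to safety reporting. A convulsion or blood dyscrasia without hospitalisation may be graded non-serious, with the 24-hour notice, SAE listing and SAE narrative delayed or missed, although the adverse event record itself remains. This assumes that some sites are guided by the example rather than by the general clause, which the documents can neither confirm nor rule out. Few such events are expected. The primary endpoint, analysis populations, power and sample size do not depend on this text.

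**What to change.** Reconcile the two sections by aligning the 8.1.1.3 example with its own lead sentence and with the regulatory text quoted in 8.1.3.2. Notify sites of the corrected wording, and check that the guidance accompanying the SAE form carries the same text.

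The cost is a one-line protocol correction and a site memo. SAP 3.8.2 needs no change, because it gives no example.

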8.1.1.4 Unexpected Adverse Drug Reactions

All AEs should be reported, whether or not they are considered to be related to the treatment. The report of AEs should include date of onset, description of the AE, severity, relation to study medication, action taken, outcome, and date of resolution. This information is needed to determine if the incidence and severity of adverse reactions is different between the test articles.

8.1.2 Assessing Intensity and Relationship of Adverse Events

8.1.2.1 Intensity

The intensity of the AE will be characterized as mild, moderate, or severe using the following criteria:

- Mild: Subject was aware of the event, but was still able to do all activities
- Moderate: Subject had to discontinue some activities due to the event
- Severe: Subject was incapacitated by the event and unable to perform normal activities

8.1.2.2 Relationship to Study Drug

The site investigator is responsible for assessing the relationship between the AE and the study product. The investigator must determine whether there is a reasonable possibility that the study product caused or contributed to an AE. The relationship assessment, based on clinical judgment, often relies on the following:

- A temporal relationship between the event and administration of study product

- A plausible biological mechanism for the study product to cause the AE
- Another possible etiology of the AE
- Previous report of similar AEs associated with the study product or other agents in the same class

The terms used to assess the relationship of an AE to study drug are included in Table 4.

Table 4 Assessment of Causality and Relationship to Study Drug

Causality Assessment	Criteria for Assessment (note that re-challenge will not be done in this study)
Related	The experience occurs immediately following study drug administration, related pharmacologically (not related to underlying condition/concurrent disease or other drugs or chemicals) and follows a known response pattern to the study drug.
Possibly Related	The experience follows a reasonable temporal sequence from the time of drug administration and/or follows a known response pattern to the trial drug but could have been produced by other factors such as the participant's clinical state, therapeutic intervention or concomitant therapy.
Not Related	There is not a reasonable possibility that the AE is related to the study product; when an AE is assessed as not related to the study product, an alternative etiology, diagnosis or explanation for the AE should be documented. If new information becomes available, the relationship of any AE should be reviewed again and updated, as required.

8.1.3 Reporting Procedures and Requirements for Adverse Events

8.1.3.1 Study Reporting Period for Adverse Events

At every visit or contact, study staff will ask each participant how she felt since her last visit and indirectly ask if she has experienced any AEs.

The reporting period for AEs is the period immediately following the signing of the ICF through 30 days after last use of study product.

For the purposes of study analysis, if a non-serious AE has not resolved at the end of the study-reporting period it will be reported as still ongoing in the EDC system. However, the investigator must make every reasonable effort to follow the event to resolution or stabilization and report to [REDACTED].

SAEs must be followed until resolution. Resolution of an SAE is defined as the return to baseline status or stabilization of the condition with the expectation that it will remain chronic.

8.1.3.2 Recording of Adverse Events

AEs will be reported in the EDC system using a recognized medical term or diagnosis that accurately reflects the event. Information recorded in the EDC system must be substantiated in the source documents. All AEs must be recorded in the participant's source documents and must include the following information (when applicable):

- Specific condition or event.
- Possible etiologies and whether the event meets criteria as an SAE and therefore requires immediate notification to the sponsor. (See [Section 8.1.1.3](#) for the definition of SAEs.)
- Indication of whether the condition was preexisting prior to study entry or not and if yes, whether it has worsened in severity or frequency, in which case it is reported as an AE. Conditions present prior to study entry that do not worsen in severity are not considered AEs.
- Date of occurrence.
- Date of resolution. If the event has not resolved at the end of the study-reporting period, it will be reported as still present in the EDC system.
- AEs that change in intensity are recorded at the most severe intensity level that is reported by the participant.
- Relationship to study product as evaluated by the investigator (causality assessment).
- Action taken with the study product per the investigator medical judgment (study product interrupted, discontinued or none) and outcome.
- Seriousness: An SAE, in accordance with 21 CFR 312.32 (a), means “any adverse event occurring at any dose that results in any of the following outcomes: death, a life threatening adverse drug experience, inpatient hospitalization or prolongation of existing hospitalization, a persistent or significant disability/incapacity or a congenital anomaly/birth defect. Important medical events that may not result in death, be life-threatening or require hospitalization may be considered a serious adverse drug experience when, based upon appropriate medical judgment, they may jeopardize the patient or subject and may require medical or surgical intervention to prevent one of the outcomes listed in this definition. Examples of such medical events include allergic bronchospasm requiring intensive treatment in an emergency room or at home, blood dyscrasias or convulsions that do not result in inpatient hospitalization or development of drug dependency or drug abuse.” In addition, cancer and drug overdose are included in [REDACTED] classification of an SAE.

8.1.3.3 Notification to Sponsor of Serious Adverse Events

All SAEs will be reported promptly in accordance with the FDA regulations and recorded on the appropriate forms.

**WHEN ANY SAE, REGARDLESS OF RELATIONSHIP TO THE STUDY PRODUCT, IS
ENCOUNTERED DURING THIS CLINICAL TRIAL AT AN INVESTIGATOR'S SITE,
THE INVESTIGATOR, IN ACCORDANCE WITH 21 CFR 312.64(b), MUST NOTIFY
[REDACTED] WITHIN 24 HOURS OF IDENTIFICATION/AWARENESS OF
THE SAE BY REPORTING THE EVENT VIA THE EDC SYSTEM AND VIA THE SAE
REPORTING FORM FOR THIS STUDY. SAE SUBMISSION SHOULD BE
COMPLETED FOR ANY SAE THAT IS EXPERIENCED AFTER THE SUBJECT HAS
SIGNED THE ICF, EVEN IF INVESTIGATIONAL PRODUCT HAS NOT YET BE
ADMINISTERED.**

The investigator should complete the AE eCRF within the EDC system and mark the AE as serious which will send the appropriate notifications to the Medical Monitor as well as the appropriate [REDACTED] staff. The clinical investigator is to also send an SAE Report Form by email to [REDACTED]

All SAEs whether or not thought related to the study drug, must be reported by the Study Investigator (by telephone, fax or email) to [REDACTED] within 24 hours of the investigator becoming aware of the event.

SAE reports should be sent to:

The investigator or responsible site staff will enter all AEs into the eCRF as delineated above. AEs that are assessed as serious also require the completion of a separate SAE report. Following receipt of the SAE report, the SAE reporting contact will review.

Additional supporting documentation for SAEs (i.e. hospital discharge summary, lab report, etc.) which should be provided whenever possible (with participant name redacted) to verify the medical diagnosis includes hospital discharge summaries and death certificates/autopsy reports (where applicable), surgical procedure summaries, histology reports, and imaging reports should be uploaded to the study document repository or [REDACTED] EDC page as outlined in the Study Procedures Manual within three days of receipt at the site. [REDACTED] will ensure appropriate copies of supporting document are provided to the Medical Monitor.

NOTE: Investigators should not wait to collect the additional information needed to fully document the event before submission of an SAE.

The SAE report will be sent immediately to the Sponsor for assessment and report to health authorities where appropriate. Treatment or laboratory tests will be conducted at the discretion of the Investigator.

